9.6.7 Selection of Doses in the Study

For Part 1, the planned doses of TD139 to be studied are: 0.15mg, 1.5mg, 3mg, 10mg, 20mg and 50mg. The maximum dose of TD139 (50 mg) will not be exceeded.

The planned dose levels have been selected following review of non-clinical pharmacokinetic, safety pharmacology and toxicology data.

Pharmacokinetic, toxicokinetic and toxicology studies in mice, rats and dogs indicate the drug is readily bioavailable via the inhaled route with little or no accumulation after 14-day dosing and is excreted in the faeces with a $t_{1/2}$ of approximately 6 h. The human starting dose is 0.15mg. Given the NOAEL's in mouse and dog studies, this FIM dose is over 100-fold below the industry accepted safe starting dose. Given the lack of adverse effects seen in the two species, no direct anticipated adverse drug specific side effects are expected in man nor are any drug interactions anticipated given the clear cytochrome profiling. Further details regarding non-clinical pharmacokinetic, safety pharmacology and toxicology data can be found in the IB^[11].

GB-HV-01 Clinical Study Protocol Confidential RD 676/25641 Version: FINAL 6.0 / 05 April 2016 Page 44 of 73

If unacceptable safety findings are identified or if there is any indication that it is not possible to maintain an ample safety margin with higher doses in subsequent cohorts the dose escalation will be stopped or modified accordingly. Subsequent doses therefore may vary from those planned depending on safety and pharmacokinetic results. If the dose escalation stopping criteria for Part 1 in section 9.2.3 are met, then the dose level that was tested will not be repeated or exceeded, however a lower dose may be given following discussion between the Sponsor and the Investigator.

The selection of the 3mg starting dose for **Part 2** was determined based upon interim safety and PK data from **Part 1** (in single doses up to 10mg) and on pre-clinical efficacy and safety data. The highest acceptable dose level in Part 1 of the study will not be exceeded in Part 2.

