- 7. Spirometry to be performed on Day 14 **prior** to BAL sampling procedure.
- 8. Subjects will be dosed with the IMP at the Clinical Centre during clinic visits and will self administer the IMP on non clinic visit days.
- 9. PK blood sampling will be taken on Day 1 prior to dosing = 0h and then at 15min, 30min, 45min, 1h, 2h, 3h, 4h, 5h, 6h and 12h post-dose; Day 2, 3 and 7 prior to dosing = 0h; Day 14 prior to dosing = 0h and then at 15min, 30min, 45min, 1h, 2h, 3h, 4h, 5h, 6h, 12h and 24h post-dose.
- 10. Blood sampling for pharmacogenetic analysis (mRNA) and peripheral blood flow cytometry will be taken Day 1 prior to dosing = 0h and then at 30 min post-dose, Day 7 at 2h post-dose and Day 14 prior to dosing = 0h and then at 30 min post-dose.
- 11. Blood sampling for pharmacogenetic analysis of peripheral blood mononuclear cells (PBMCs) will be taken Day 1 prior to dosing = 0h and Day 14 at 30 min post-dose.
- 12. Blood sampling for Galectin-3 analysis will be taken on Day 1 prior to dosing = 0h and then at 5h post-dose, Day 7 (anytime) and Day 14 prior to dosing = 0h.
- 13. Exhaled Breath Condensate to be performed on Day 14 between 1h and 2h post-dose.
- 14. BAL to be performed on Day 14 between 1h and 4h post-dose. (It is essential post treatment bronchoscopy is performed in the morning.)

GB-HV-01 Clinical Study Protocol Confidential RD 676/25641 Version: FINAL 6.0 / 05 April 2016 Page 51 of 73

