The same analysis will be carried out (for C_{max} , AUC_{τ} , $t\frac{1}{2}$ and CL/F) for Part 2 of the study on Days 1, 7 and 14.

GB-HV-01 Clinical Study Protocol Confidential RD 676/25641 Version: FINAL 6.0 / 05 April 2016 Page 62 of 73

Accumulation Assessment: Log-transformed trough levels at pre-dose on Day 2 through to Day 14 will be used to establish any accumulation of TD139. The ratio of trough concentrations on each consecutive day will be presented and summarized along with a 90% confidence interval. The analysis will be done for each dose level.

Assessment of Steady State: Log-transformed trough concentration levels at pre-dose on Days 7, and 14 will be subjected to mixed effects ANOVA with study day as a fixed effect and subject as a random effect in order to establish whether and when steady state has been attained for each dose level. Back-transformed ratios for the Day 14/Day 7, comparisons will be presented along with corresponding 90% CI.

Additional PK Assessments:

Alveolar macrophage and BAL fluid concentrations of TD139 will be presented as a data listing.

Drug compartment measurements in BAL and alveolar macrophages will be analysed as per the method set out in the study by Naderer *et al*^[1] (e.g. TD139AM = TD139pellet/VAC [where the volume of alveolar cells - VAC, is estimated at 2.42μ l/106 cells])^[1].

PD Assessments:

Macrophage morphology parameters (*ex-vivo* macrophage function and BAL soluble markers) will be presented as a data listing.

Exhaled breath condensate data will be presented as a data listing.

Descriptive statistics of absolute and change from baseline for peripheral blood flow cytometry data will be presented at each time point by dose.

Descriptive statistics of absolute and change from baseline for Galectin-3 plasma concentration data will be presented at each time point by dose.

PG Assessments:

Macrophage phenotypic, mRNA pattern expression analysis from BAL and analysis of peripheral blood mononuclear cells for IPF gene signatures will be presented as a data listing.

Descriptive statistics of absolute and change from baseline of mRNA expression levels from blood leucocytes will be presented at each time point by dose.

Safety Assessments:

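### Accumulation in Part 2 is tied to ratios of successive troughs, which describe the approach to steady state; no planned ratio compares Day 14 with first-dose exposure

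*Protocol*

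**What the plan says.** Protocol section 9.9.1.3, Accumulation Assessment, names the data: "Log-transformed trough levels at pre-dose on Day 2 through to Day 14 will be used to establish any accumulation of TD139". It then names the statistic: "The ratio of trough concentrations on each consecutive day will be presented and summarized along with a 90% confidence interval". The analysis is done separately for each dose level.

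The next paragraph, on steady state, is a separate mixed-model analysis of the Day 7 and Day 14 troughs: "Back-transformed ratios for the Day 14/Day 7, comparisons will be presented along with corresponding 90% CI".

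The sampling times are in Table 9.7.2, footnote 9. Day 1 has a rich profile ("PK blood sampling will be taken on Day 1 prior to dosing = 0h and then at 15min, 30min, 45min", continuing to 12 h). The pre-dose samples that follow are "Day 2, 3 and 7 prior to dosing = 0h; Day 14 prior to dosing = 0h", and the Day 14 profile runs to 24 h. The Day 2 pre-dose sample can serve as the 24 h point of the Day 1 profile.

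Section 9.9.1.3 also repeats the dose regressions of Cmax, AUC over the dosing interval, half-life and clearance "for Part 2 of the study on Days 1, 7 and 14". These compare doses, not days. AUC0-tau is a listed variable in section 9.9.1.1; an accumulation ratio is not. The only half-life given is non-clinical, about 6 h, in section 9.6.7, which reports "little or no accumulation after 14-day dosing" in animals.

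**The concern.** Accumulation compares exposure after repeat dosing with exposure after the first dose. A ratio of one trough to the preceding one measures a single step of the climb between them, and the later steps flatten towards 1 once steady state is near. The protocol therefore names a statistic that does not measure what it is said to establish.

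The schedule adds a second difficulty. Among Days 2, 3, 7 and 14 only the first two are consecutive. Read literally, the plan yields one ratio. Read as successive samples, it yields three ratios over unequal gaps of 1, 4 and 7 days, and the last of these, Day 14/Day 7, is already the steady-state statistic.

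Part 2 is the step from single to 14-day dosing, and multiple-dose PK is a secondary objective (section 8.2). The exposure limits in section 9.2.3 are set in Cmax and AUC, so a trough ratio is not on the scale that the protocol itself uses for exposure.

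**Working it through.** The protocol states no accumulation figure or threshold, so there is none to reproduce. The check asks what each planned ratio would show for a known accumulation.

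**Inputs.** Dosing interval 24 h, 14 daily doses (section 9.1). Troughs on Days 2, 3, 7 and 14 (Table 9.7.2, footnote 9). Half-life about 6 h in animals (section 9.6.7). The human half-life is not given, so 6 to 72 h is assumed as a range.

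**Model.** Linear kinetics, one compartment, rapid absorption. Let x = 2^(-24/t½).

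- Trough on Day d is proportional to 1 - x^(d-1).
- Day 3/Day 2 = (1 - x²)/(1 - x) = 1 + x, which cannot exceed 2.
- Day 7/Day 3 = (1 - x⁶)/(1 - x²).
- Day 14/Day 7 = (1 - x¹³)/(1 - x⁶).
- Steady-state accumulation factor R = 1/(1 - x).
- AUC0-tau Day 14/Day 1 = (1 - x¹⁴)/(1 - x).

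**Example, 24 h.** x = 0.5. R = 1/0.5 = 2.00. Day 3/Day 2 = 1.50. Day 7/Day 3 = 0.984/0.750 = 1.31. Day 14/Day 7 = 1.000/0.984 = 1.02.

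| Half-life (h) | R | Day 3/2 | Day 7/3 | Day 14/7 | Product = Day 14/2 | AUC0-tau Day 14/1 |
|---|---|---|---|---|---|---|
| 6 | 1.07 | 1.06 | 1.00 | 1.00 | 1.07 | 1.07 |
| 12 | 1.33 | 1.25 | 1.07 | 1.00 | 1.33 | 1.33 |
| 24 | 2.00 | 1.50 | 1.31 | 1.02 | 2.00 | 2.00 |
| 48 | 3.41 | 1.71 | 1.75 | 1.13 | 3.38 | 3.39 |
| 72 | 4.85 | 1.79 | 2.03 | 1.27 | 4.61 | 4.66 |

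From 12 h upwards no single successive ratio gives R; at 6 h the Day 3/Day 2 ratio nearly does. The product of the three, and the AUC ratio, give R or come close to it.

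**Troughs against exposure.** In one compartment, Day 14/Day 2 and the AUC ratio agree closely. With two compartments they need not. If 90% of the initial concentration falls with a 6 h half-life and 10% with 48 h (assumed values), trough Day 14/Day 2 is 2.35 while AUC0-tau Day 14/Day 1 is 1.57. That is why the trough ratio belongs in a supportive place.

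**The case against.** The strongest reply has four parts, and much of it stands.

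- **The early ratios do carry information.** A reader might infer that successive ratios shrink to 1 whatever the accumulation. The table does not support that: at 48 h they go from 1.71 to 1.75 before falling to 1.13. A Day 3/Day 2 interval above 1 would signal accumulation. What such a ratio does not give is its extent.
- **Doubled exposure would not be hidden.** A reader might also infer that a two-fold build-up would go unseen. The documents do not support that either. Multiplying the ratios gives Day 14/Day 2 (1.50 × 1.31 × 1.02 = 2.00 after rounding). Derived PK parameters are summarised, and the interim reviews receive Cmax and AUC directly (section 9.2.2). What is missing is a planned between-day ratio with an interval.
- **The wording might mean each trough against the first.** That reading would include Day 14/Day 2, but the text does not say so.
- **Detail may be left to the SAP.** Section 9.9.1.3 does defer full details. However, it already fixes the data, the statistic and the interval for accumulation, so this is more than an omitted detail.

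Two further arguments against troughs should not be pressed. Home-dose timing can affect only the Day 7 and Day 14 troughs, because the doses on Days 1 and 2 are given at the clinic. A precision advantage for AUC would need within-subject CVs that the protocol does not give. With 5 active subjects, the 90% CI factor for a paired ratio runs from 1.31 (CV 20%) through 1.49 (30%) to 1.89 (50%). Which measure has which CV is unknown.

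**Conclusion.** The point holds as a fault in the choice of statistic. Section 9.9.1.3 assigns to successive-trough ratios a question that they do not answer, and the schedule supplies only one literally consecutive pair. The Day 1 and Day 14 profiles, which do answer it, are not compared between days.

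The size turns on the human half-life. Near 6 h the factor is about 1.07 and Day 3/Day 2 would already read 1.06, so almost nothing is lost. At an assumed 24 h the factor is 2.00 against 1.50, 1.31 and 1.02; at an assumed 48 h it is 3.41 against 1.71, 1.75 and 1.13. These figures rest on linear one-compartment kinetics, and nothing in the protocol shows that the longer half-lives apply.

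This concerns a secondary PK objective. It touches neither the primary safety analysis nor the exposure stopping limits. It is worth correcting because the correction is nearly free.

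**What to change.** Rewrite the accumulation paragraph of section 9.9.1.3:

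- Define accumulation as the within-subject ratios AUC0-tau Day 14/Day 1 and Cmax Day 14/Day 1, analysed on the log scale and reported as geometric mean ratios with 90% CI for each dose level.
- State that the Day 2 pre-dose sample is the 24 h point of the Day 1 profile.
- Give trough Day 14/Day 2 with 90% CI as supportive.
- Relabel the successive-trough ratios as approach to steady state, and name the pairs actually sampled: Day 3/Day 2, Day 7/Day 3 and Day 14/Day 7.
- Add the accumulation ratios to the variables in section 9.9.1.1.

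Pooling over dose levels is optional. The cost is a change of wording and a few more table rows; every sample needed is already scheduled.

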Galecto Biotech has developed a novel IPF treatment (TD139) that acts as a Galectin-3 (Gal-3) inhibitor. TD139 has been inhibitor developed as a dry powder for inhalation (DPI) for the indication "Treatment of adults with Idiopathic Pulmonary Fibrosis" (IPF). The chemical name is Bis-(3-deoxy-3-(4-(3-fluorophenyl)-1H-1,2,3-triazol-1-yl)- β -D-galactopyranosyl) sulfane. Galectin-3 is a member of the lectin family of carbohydrate-binding proteins and it is implicated in a number of cellular processes, including cell adhesion, cell activation, chemo-attraction, cell growth, differentiation and apoptosis. Galectin-3 binds to itself and to TGF β receptors, forming lattices that hold the receptors at the cell surface thus altering TGF β signal transduction. TGF β signalling is thought to drive many of the processes associated with fibrosis and inhibiting this pathway should reduce IPF disease progression.

Clinical Study Protocol

RD 676/25641 Version: FINAL 6.0 / 05 April 2016 Page 24 of 73

In this trial, TD139 will be studied to explore its safety and tolerability in healthy volunteers and subsequently safety and tolerability in patients with IPF whilst pharmacodynamic measurements from samples taken from the lung in these patients before and after 14 days of treatment with TD139 may help to establish a proof of mechanism for TD139.

Further details regarding the mechanism of action of TD139, including safety data and a summary of the known and potential risks and benefits can be found in the IB^[11]. A separate interim report (Interim Report Part 1, v1.0 28 Nov 2014), summarising safety and PK up to the 10mg doses of TD139 in healthy volunteers has been written. All adverse events were mild and self-limiting and there were no significant changes from baseline in any of the following parameters; ECG, vital signs, biochemistry, haematology and urinalysis.

Clinical Study Protocol

RD 676/25641 Version: FINAL 6.0 / 05 April 2016 Page 25 of 73

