This study will be divided into 2 parts. **Part 1** is a randomised, double-blind, single centre, placebo-controlled, SAD, phase I study designed to assess the safety, tolerability, PK and PD of TD139 in up to 36 healthy male subjects.

Part 1 of this study employs a single ascending dose design; corresponding placebo control will be administered in order to evaluate treatment-related effects.

The design of **Part 1** of this study is typical of that used for FIM studies with a "dose leader" design for built-in safety. A dose leader design will be implemented in which 2 subjects (1

GB-HV-01 Clinical Study Protocol

RD 676/25641 Version: FINAL 6.0 / 05 April 2016 Page 33 of 73

TD139 and 1 placebo) in each cohort will be dosed approximately 24 hours before the rest of the Cohort. Providing there have been no safety concerns in the dose leader group up to the 24 hour time point, the remainder of the cohort (4 subjects) will be dosed a day later and will be randomised in such a way that one further subject receives placebo. This design allows maintenance of the "blind".

Safety and PK data from a minimum of 5 subjects of each cohort will be required for data review prior to dose escalation.

Part 2 will be a randomised, double-blind, multi-centre, placebo-controlled, multiple dose expansion cohort study designed to assess the safety, tolerability, PK and PD of TD139 in up to 24 male and female subjects of non child-bearing potential with IPF.

This part of the study will consist of 1 cohort of up to 24 IPF subjects, who will receive a single dose of TD139 or placebo via DPI once daily for 14 days (TD139 and placebo dosed according to **Table S1**). The initial dose level used will be 3mg based on PK and safety data from **Part 1** and on pre-clinical efficacy and safety data.

During **Part 2** there will be an interim review by the safety committee after 8 subjects have been dosed to review the available blinded safety and PK data. The initial 8 subjects will be randomised in such a way that 5 will receive TD139 and 3 will receive placebo. Following a review of this data a decision will made as to whether to randomise up to 4 further subjects (where 3 subjects will receive TD139 and 1 will receive placebo) in Cohort 1 or move on to a second dose level in Cohort 2 (see Table S1). The dose and PK sampling times may also be modified following a review of the data.

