9.9 Statistical Methods and Determination of Sample Size

9.9.1 Statistical and Analytical Plan

9.9.1.1 Primary and Secondary Variables for Assessment

The primary safety assessment variables will be the vital signs data, ECG data, laboratory data and the adverse events reported.

The secondary pharmacokinetic variables will be the following non-compartmental pharmacokinetic end-points:

	Politica
• C _{max}	Maximum plasma concentration
• t _{max}	The time to maximum observed concentration sampled during
	a dosing interval
 λ_z 	Elimination rate constant
• t _{1/2}	Terminal half-life
• AUC _{0-t}	Area under the plasma concentration-time curve (AUC) from the
	time of dosing to the time of the last observed concentration
• AUC _{0-τ}	Area under the plasma concentration-time curve (AUC) from the
	time of dosing to time t at steady state
• AUC _{0-inf}	The area under the curve (AUC) extrapolated to infinity from dosing
	time, based on the last observed concentration
• CL/F	Plasma clearance, calculated as Dose / $AUC_{0\text{-}inf}$
AUC% extrapolated	Residual area

The secondary pharmacodynamic variables will be the peripheral blood flow cytometry data and galectin-3 plasma concentration data.

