Vital signs parameters will be listed with any out of normal range values flagged. Descriptive statistics of absolute and change from baseline (pre-dose) supine systolic and diastolic blood pressure, supine pulse rate, respiration rate, oral temperature and O_2 saturation at each time point, up to and including Day 15, will be tabulated by dose.

The mean change from baseline data will also be plotted by dose across time, up to and including Day 15.

12-Lead ECG parameters will be listed with any out of normal range values flagged. Descriptive statistics of absolute and change from baseline (pre-dose) heart rate, PR interval, QRS interval, QT interval and QTcB interval at each time point, up to and including day 15, will be tabulated by dose.

Confidential Page 63 of 73

The mean change from baseline data will also be plotted by dose across time, up to and including Day 15.

In addition, frequencies of QTcB data will be calculated according to the following categories:

For absolute values

- OTcB > 450 mSec
- QTcB > 480 mSec
- QTcB > 500 mSec

For change from baseline

- QTcB increase > 30 mSec
- QTcB increase > 60 mSec

All adverse events will be coded using the MedDRA dictionary, version 16.1.

All adverse events, including those that occur prior to the first administration of the study drug, will be listed. Only treatment-emergent adverse events (TEAEs), i.e. existing conditions that worsen or events that occur during the course of the study after administration of study drug, will be included within the summary tables. Adverse event summaries will be presented by treatment and overall (data from all dose groups will be pooled).

An overall summary of adverse events will be produced including the number of TEAEs; the number and percentage of subjects reporting at least one: TEAE, serious TEAE, TEAE leading to withdrawal from the study; the number and percentage of subjects reporting TEAEs by severity and relationship to study drug.

The number of TEAEs and the number and percentage of subjects reporting at least one TEAE will be tabulated by system organ class (SOC) and preferred term (PT). A subject reporting multiple episodes of a particular adverse event within a study period will only contribute one count towards the corresponding system organ class and preferred term within that study period.

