In addition, the number and percentage of subjects reporting TEAEs will be tabulated by maximum severity and strongest relationship to study drug. For the summary of TEAEs by severity, if a subject has multiple events occurring within the same SOC or preferred term, the event with the highest severity will be counted. Similarly, for TEAEs by relationship to study drug, if a subject has multiple events occurring within the same SOC or preferred term, the event with the highest association to study drug will be counted.

Biochemistry, haematology and urinalysis parameters will be listed with any out of normal range values flagged. Laboratory test results that are out of normal range will also be presented separately along with normal reference ranges. Descriptive statistics of absolute and change from baseline (pre-dose) values for each biochemistry and haematology parameter at each time point, up to and including day 15, will be tabulated by dose.

GB-HV-01 Clinical Study Protocol Confidential RD 676/25641 Version: FINAL 6.0 / 05 April 2016 Page 64 of 73

Frequencies of the total number of subjects randomised, completed, and prematurely discontinued (including reason for discontinuation) from the study will be summarised by dose. Additionally the frequency of subjects within each analysis population (safety, PK) will be summarised by dose.

Demographic data will be listed and descriptive statistics will be tabulated for the continuous variables age, height, weight and BMI and frequencies for the categorical variable race. These descriptive statistics will be presented by dose and overall.

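### Blood PD markers and leucocyte mRNA are summarised only as within-dose change: no TD139-minus-placebo estimate is planned, and pooling of placebo over cohorts is not stated

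*Protocol*

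**What the plan says.** Protocol section 9.9.1.1 names the secondary PD variables: "The secondary pharmacodynamic variables will be the peripheral blood flow cytometry data and galectin-3 plasma concentration data". Section 9.9.1.3 then fixes their output. For galectin-3, "Descriptive statistics of absolute and change from baseline for Galectin-3 plasma concentration data will be presented at each time point by dose". For flow cytometry, "Descriptive statistics of absolute and change from baseline for peripheral blood flow cytometry data will be presented at each time point by dose". Leucocyte mRNA is treated in the same way under the PG assessments.

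The section gives no difference between TD139 and placebo for any of these markers, and it does not say how the placebo subjects of successive cohorts are shown. For PK, the same section specifies a power model with 95% intervals, a mixed-effects ANOVA and 90% intervals.

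Three other places bear on the point:
- Section 9.3 gives the reason for placebo in Part 1: "corresponding placebo control will be administered in order to evaluate treatment-related effects".
- Section 9.9.2 calls the Part 2 PD measurements exploratory and says they will inform a Phase 2b study.
- The synopsis tabulates safety parameters by treatment group, whereas section 9.9.1.3 presents numeric safety and PD data by dose.

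**The concern.** A change from baseline within one dose contains everything that moves the marker over time, not only the drug. The schedule builds in several influences that both arms share:

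- **Part 1, galectin-3.** The pre-dose sample follows a fast of at least 10 hours. The later Day 1 sample is at 5 hours, one hour after lunch at 4 hours (section 9.5.3.1; Table 9.7.1, footnote 8).
- **Part 1, flow cytometry and mRNA.** With dosing at about 9 a.m., the 18-hour sample falls at about 3 a.m. (section 9.6.8; Table 9.7.1, footnote 7).
- **Part 2, flow cytometry and mRNA.** The Day 1 pre-dose sample comes one day after the Day -1 lavage (Table 9.7.2 and footnote 10).

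The protocol does not say how large these influences are. In expectation they cancel in the comparison of randomised arms, which is what the placebo subjects are there to provide. As written, the reader of the tables has to form that comparison by eye, possibly against only 2 or 3 placebo subjects per cohort. A Phase 2b design needs the between-arm difference and its uncertainty, and neither is a planned output.

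**Working it through.** The protocol states no sample size calculation, power, SD or effect size for these markers, so there is no figure to reproduce. What can be checked is how many subjects a contrast would have and how precise it would be.

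**Allocation (synopsis, sections 9.1 and 9.6.6), TD139 : placebo**
- Part 1, six cohorts of 4:2: 24 : 12.
- Part 2, Outcome 1, three cohorts of 5:3: 15 : 9.
- Outcome 2, 5+5+3 : 3+3+1 = 13 : 7.
- Outcome 3, 5+3+5 : 3+1+3 = 13 : 7.
- Outcome 4, 5+3+5+3 : 3+1+3+1 = 16 : 8.

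**Precision.** In units of the SD of change, the 95% CI half-width for a difference of two means is

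t(0.975, n1+n2−2) × √(1/n1 + 1/n2).

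For 5 v 9: 2.179 × √(1/5 + 1/9) = 2.179 × 0.558 = 1.22. The other comparisons follow in the same way.

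| Comparison | n1 v n2 | Half-width (SD of change) |
|---|---|---|
| Part 1, one dose v its own cohort's placebo | 4 v 2 | 2.40 |
| Part 1, one dose v pooled placebo | 4 v 12 | 1.24 |
| Part 1, all TD139 v pooled placebo | 24 v 12 | 0.72 |
| Part 2, one dose v its own cohort's placebo | 5 v 3 | 1.79 |
| Part 2 Outcome 1, one dose v pooled placebo | 5 v 9 | 1.22 |
| Part 2 Outcome 1, all TD139 v pooled placebo | 15 v 9 | 0.87 |
| Part 2 Outcomes 2 and 3, all TD139 v pooled placebo | 13 v 7 | 0.98 |
| Part 2 Outcome 4, all TD139 v pooled placebo | 16 v 8 | 0.90 |

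**What pooling is worth.** For a single dose, going from own-cohort to pooled placebo shortens the half-width by 1 − 1.22/1.79 = 32% in Part 2 and by 1 − 1.24/2.40 = 48% in Part 1. Whether placebo is pooled therefore matters.

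These half-widths are for an unadjusted two-sample comparison with equal variances. Adjusting for baseline costs one degree of freedom and may reduce the residual SD. The protocol gives nothing from which to judge by how much.

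**The case against.** The case for leaving the text alone has real force.

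1. **The SAP.** Section 9.9.1.3 leaves full analysis details to a statistical analysis plan, which is not at hand. A covariance model and a rule for pooling placebo often belong there, and descriptive tables in the protocol do not rule them out. This stands as a limit: the point concerns what the protocol fixes, and it is closed if the SAP already has the contrast. But the section did choose models and intervals for PK and description for PD.

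2. **Placebo is probably visible.** A reader might infer that *by dose* leaves placebo out. The documents do not support that. Section 9.9.1.2 puts placebo subjects in the safety set, section 9.9.1.3 counts randomised subjects and analysis populations by dose, adverse events are given by treatment, and the synopsis uses treatment groups for safety. A placebo column is the natural reading, and absolute values are tabulated as well as change.

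3. **No within-arm test is planned.** A reader might attach a false-positive rate to the within-dose change. That would describe a decision rule the protocol does not contain.

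4. **Exploratory status.** Part 2 PD is declared exploratory, and no stopping rule in section 9.2.3 uses PD change. Description is a legitimate choice at this stage, and the intervals would be wide.

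Points 2 to 4 reduce the matter to an improvement. They do not supply the missing estimate or the missing statement on pooling.

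**Conclusion.** The point holds as a modest, inexpensive improvement to the PD analysis. For galectin-3, blood flow cytometry and leucocyte mRNA, the protocol randomises subjects to placebo but plans no placebo-adjusted estimate, and it does not say how placebo is combined. The estimate would be imprecise. In Part 2 its half-width is about 1.2 SD of change for one dose and 0.9 to 1.0 SD for all TD139; in Part 1 it is about 1.2 and 0.7 SD. It therefore supports estimation only. These figures assume complete data, equal variances, full cohorts and, for the single-dose Part 2 figure, Outcome 1.

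Three stronger readings are not supported:
- **That the safety analysis is at fault.** Numeric safety is also given as change by dose (for example "The mean change from baseline data will also be plotted by dose across time, up to and including Day 15"), but the synopsis's treatment groups and the safety set make a placebo column clear there.
- **That proof of mechanism rests on before-and-after change in these markers.** The introduction's phrase "before and after 14 days of treatment with TD139 may help to establish a proof of mechanism for TD139" concerns samples from the lung, and the lavage results are to be listed. It does not bear on the blood markers.
- **That the second lavage contaminates the on-treatment values.** The Day 14 lavage is 1 to 4 hours after dosing. On Day 14 galectin-3 is taken pre-dose, and flow cytometry and mRNA pre-dose and at 30 minutes (Table 9.7.2, footnotes 10, 12 and 14). It comes after every on-treatment sample of these markers.

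**What to change.** In section 9.9.1.3, or in the SAP with a cross-reference:

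1. Keep the descriptive tables.
2. State that placebo is shown as its own group, pooled over cohorts within each Part, with a listing by cohort beside it. Align the by-dose wording with the synopsis's treatment groups.
3. For galectin-3, flow cytometry and leucocyte mRNA, add the TD139-minus-placebo difference in change from baseline, adjusted for the baseline value, with a 95% CI. Give it for each dose and for all TD139 combined, separately for each Part.
4. Label it exploratory estimation, with no hypothesis test.

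The cost is one paragraph and a few tables; no subjects, visits or samples are added. There are two downsides. The intervals will be wide and should be expected to be so. Pooling assumes that placebo subjects are comparable across cohorts, which the by-cohort listing lets the reader inspect.
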